4. SELECTION OF TRIAL POPULATION

Healing chronic ulcers will have a positive impact on patient well-being and quality of life. In this study we aim to examine the efficacy of Topical Wound Oxygen (TWO₂) therapy with AMWT in the healing of diabetic foot ulcers and compare the outcome to that of AMWT and Control therapy in a double blind study.

In the event that a subject being considered for study enrollment has multiple diabetic foot ulcers, the ulcer to be considered as the index ulcer will be the largest one, which still meets all other inclusion criteria (Index ulcer).

4.1. Inclusion Criteria

A subject must meet all of the following criteria to be eligible for enrollment in the trial.

Ulcer characteristics

- Subject has a documented diagnosis of Diabetes mellitus Type 1 or 2
- Foot ulcer at or below ankle with duration of more than 4 weeks but no longer than 1 year
- If the index ulcer is a post amputation wound date of surgery must be > 30 days
- 2 week run in period with less than 30% wound size reduction
- University of Texas Grade 1A, 1B, 1C, 1D, 2A, 2B, 2C, or 2D (Appendix I)
- Ulcer is $\geq 1\text{cm}^2$ and $\leq 20\text{cm}^2$ after debridement at start of run-in period
- If more than one ulcer is present on the foot, only the largest is considered in the study (Index ulcer)
- Index ulcer must be $\geq 1\text{cm}$ away from any other ulcers present on the foot

Vascular status

- Adequate perfusion with ABI > 0.7 **And**
TcPO₂ > 30mmHg **OR** skin perfusion > 30mmHg **OR** Toe pressure > 30mmHg **OR**
Duplex with biphasic waveforms below the knee
- No planned revascularization procedure or vascular surgery within the last/next 30 days

Device and study related

- Males and Females 18-89 years
- Subject and/or caregiver are willing and able to comply with all specified care and visit requirements
- Subject has a reasonable expectation of completing the study; according to the Investigator's clinical judgment

4.2. Exclusion Criteria:

Ulcer characteristics

- Evidence of gangrene on any part of affected limb
- Documented evidence of osteomyelitis on any part of affected limb
- Index ulcer has exposed bone
- Index ulcer exhibits signs of severe clinical infection that requires hospitalization or immediate surgical intervention
- Active Charcot foot on the study limb

Device and study related

- Subject participated in another investigational device, drug or biological trial within last 30 days
- Uncontrolled diabetes: HbA1c > 12 %
- Renal dialysis or serum creatinine > 2.5 mg/dl
- Known immune insufficiency
- Chronic steroid use or immunosuppressive agents within the last three (3) months or is anticipated to require them during the course of the study
- Active treatment for malignancy (not specific to study limb)
- Patient has a Deep Vein Thrombosis within the last 30 days
- Subject has received growth factor therapy (e.g., autologous platelet-rich plasma gel, becaplermin, bilayered cell therapy, dermal substitute, extracellular matrix) within the screening period
- Subject may not be pregnant at the time of treatment

4.3. Removal of Subjects from Therapy or Assessment

Subjects may discontinue study treatment and withdraw from the study at any time. The reasons for withdrawal may include the subject withdrawing their consent to participate in the study, or Investigator may decide to withdraw the subject from the study because of Adverse Events and Device Effects (ADE) or subject non-compliance.

Where subjects are removed from study treatment (TWO2 therapy or Control therapy) for other than non-compliance and continue to provide consent to participate, may continue with study visits to assess for primary and secondary endpoints. This may include:

- 12 week final treatment visit
- 12 week follow up
- 38 week follow up

If treatment is terminated and no follow up visits are anticipated, the final evaluation will be performed as completely as possible. In addition, any comments (spontaneous or elicited) or complaints made by the subject and the reason for termination will be recorded in the CRF and the subject's medical records.

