
[figure not shown]
All subjects whose wounds are confirmed closed or who finished the treatment phase of 12 weeks – whichever is sooner - will enter into the post-treatment follow-up phase of 12 and 38 weeks.

Subjects who are withdrawn by the PI/Subl from the study treatment phase will be asked to return for the final week 12 on treatment visit and follow-up phase at 12 and 38 weeks.

The maximum duration for participation in the trial is 54 weeks. During the follow-up phase, subjects will receive standard care according to the clinician's recommendation and will be asked not to participate in another wound care trial in this period.

The start of the trial is scheduled for July 2014.

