- 12) Blood sample taken to obtain values for (**visit 12 only**):
 - Electrolytes
 - Creatinine
 - HbA1c, blood glucose
 - WBC
 - Albumin and pre-albumin (where available)
 - CBC
 - C-reactive protein
- 13) EQ-5D) (week 4, 8 and 12 only)
- 14) Education on diabetes management and foot care and off-loading boot/CROW boot
- 15) Dispense study dressings and diary card
- 16) Device competency assessment (completed in subject's home or equivalent. Week 4 and 8 only)

8.2.5 *Punch biopsies*

Punch biopsies may be taken at baseline and 4 weeks for up to 20 subjects enrolled in the study at selected centers. These subjects will have specifically agreed to this procedure on their Informed Consent Form.

The biopsies will be taken utilizing a standard 4 mm dermal punch biopsy kit and will be taken following routine debridement of the wounds to avoid collection of dead necrotic tissue. Prior to biopsy collection, the wound bed is prepared with local antiseptics. As per subject request, local anesthesia is administered. This is not standard because most subjects in this study will be insensate in the area of the wound.

In addition it is important to have some tissue samples without local anesthetic to determine whether the use of anesthetic agents impacts the molecular studies planned with the biopsy. Biopsies will be taken from the wound edge and from the center of the wound.

Samples will be collected, packed and transported per the procedure outlined by the testing laboratory instructions. The samples will be transported from clinic to the testing laboratory in properly secured biohazard-safe containers under appropriate temperature conditions.

The samples will be analyzed histologically for signs of infection, collagen and neo-angiogenesis. Additional immune-histochemical analyses for such values as VEG-F and matrix metalloproteinases (MMPs) are also envisioned.

8.2.6 *Premature Withdrawal of a Subject from the Trial*

Subjects are free to withdraw from the trial at any time without penalty or prejudice to their further treatment. Subjects may stop the trial treatment for any reason.

All subjects should be invited to do the End of Trial Visit to complete a final assessment, including wound status, complete quality of life questionnaire, etc.

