9.2 General Statistical Methods

Analysis Populations

Two analysis populations will be evaluated: Intent To Treat (ITT) and Per Protocol (PP). The ITT population will be considered the primary population of interest and will include all subjects who were randomized to study treatment. The PP population will include all subjects who were randomized to study treatment and had no significant protocol violations that might affect the outcome of treatment.

All participants will be followed up to the primary end point (12 weeks) irrespective of whether they were on active treatment. Participants that withdraw from treatment continue to be followed up to the 12 week end-point. Participants that die, undergo amputation or who are lost to follow up will be considered as treatment failures.

Continuous demographic variables (age, ulcer duration, etc.) will be summarized for the study population as descriptive statistics (number, mean, median, SD, minimum and maximum value), and by randomized groups. No formal inferential statistical testing will take place of baseline values in relation to randomized groups.

Categorical demographic variables, such as gender, will be summarized as a proportion of the intention-to-treat population.

All analyses will be undertaken using the STATA 11 statistical package.

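### Section 4.3 excepts subjects removed for non-compliance from continued study visits, against 3.1, 8.2.6 and 9.2, so week-12 closure and later events may be missed where a site applies it

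*Combined protocol and SAP*

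**What the plan says.** Section 4.3 (Removal of Subjects from Therapy or Assessment) says the "Investigator may decide to withdraw the subject from the study because of Adverse Events and Device Effects (ADE) or subject non-compliance". It goes on to say that subjects removed from study treatment "for other than non-compliance and continue to provide consent to participate, may continue with study visits", and lists the week-12 treatment visit and the 12- and 38-week follow-ups. It closes with a fallback: "If treatment is terminated and no follow up visits are anticipated, the final evaluation will be performed as completely as possible".

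Other sections give the follow-up rule without an exception for non-compliance:

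- Section 3.1: subjects whom the investigator withdraws from the treatment phase "will be asked to return for the final week 12 on treatment visit and follow-up phase at 12 and 38 weeks".
- Section 8.2.6: "All subjects should be invited to do the End of Trial Visit to complete a final assessment". It also asks subjects withdrawn from treatment to consent to follow-up for 12-week healing, and plans the later follow-ups wherever possible in those withdrawn.
- Section 9.2: "All participants will be followed up to the primary end point (12 weeks) irrespective of whether they were on active treatment", and "Participants that withdraw from treatment continue to be followed up to the 12 week end-point". The primary population is all randomized subjects.
- Section 9.1: the sample size is not raised for loss to follow-up, on the ground that every patient will have a 12-week outcome.

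For an outcome that is not observed, 9.2 counts loss to follow-up as treatment failure, while 9.5 imputes nothing and omits subjects with missing data.

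**The concern.** Section 4.3 is the section headed for removal from therapy or assessment, so site staff may well turn to it when a subject stops attending sessions. Read alone, it tells them that a subject removed for non-compliance is not among those who continue visits. With up to 30 centers, sites could follow different rules.

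Non-compliance with 90-minute sessions five times a week arises after randomization. It may reflect pain, skin problems, device malfunction or a worsening wound. Only the active device delivers oxygen and pressure, so the rate of removal could differ by arm despite blinding. If follow-up stops for that reason, the intention-to-treat comparison of closure rests on a selected subset or on an assumed outcome, and later amputations and new adverse events may be missed in the same subjects.

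Nor is it clear how such a subject enters the primary analysis. Section 8.2.12 reserves the term lost to follow-up for subjects not reached after at least four attempts. A contactable subject whom the site has stopped following does not plainly meet that definition, so either the failure rule in 9.2 or the omission rule in 9.5 could be applied.

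**Working it through.** **The passages side by side**

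| Section | Who is followed off treatment | Exception for non-compliance |
|---|---|---|
| 3.1 | Those withdrawn from treatment by the investigator are asked back for week 12 and both follow-ups | No |
| 4.3 | Those removed who still consent may continue | Yes |
| 8.2.6 | All invited near week 12; later follow-up wherever possible | No |
| 9.2 | All participants, to week 12 | No |

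**The plan's own figure.** Inputs from 9.1: closure 43% v 64%, power 80%, 1:1 allocation, no continuity correction, and three Pocock looks at nominal 0.022. With pooled variance and a two-sided test,

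n = [z(1−α/2)·√(2p̄(1−p̄)) + z(0.80)·√(p₁(1−p₁)+p₂(1−p₂))]² / (p₂−p₁)², where p̄ = 0.535.

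- α = 0.05: (1.960×0.7054 + 0.8416×0.6896)² / 0.21² = 87.4, so 88 per arm.
- α = 0.022: (2.290×0.7054 + 0.8416×0.6896)² / 0.21² = 109.3, so 110 per arm.

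Both match the plan. Power at 110 per arm and 0.022 is Φ[(0.21×√110 − 2.290×0.7054)/0.6896] = Φ(0.851) = 80.3%.

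**If a share q of each arm is unobserved at week 12.** The documents give no value, so q is an assumption. Failure scoring replaces the rates by 0.43(1−q) and 0.64(1−q), which assumes that these subjects would have closed at their arm's rate. Omission keeps the rates and uses 110(1−q) per arm.

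| q | Rates if failures (%) | Difference (points) | Power, failures | Power, omitted |
|---|---|---|---|---|
| 0 | 43.00 v 64.00 | 21.00 | 80.3% | 80.3% |
| 2% | 42.14 v 62.72 | 20.58 | 78.3% | 79.4% |
| 5% | 40.85 v 60.80 | 19.95 | 75.3% | 77.9% |
| 10% | 38.70 v 57.60 | 18.90 | 70.0% | 75.4% |
| 15% | 36.55 v 54.40 | 17.85 | 64.6% | 72.6% |

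These are fixed-sample powers, the basis that 9.1 uses. Simulating all three looks (37, 73 and 110 per arm, 200,000 trials) gives overall power of 84.6% at q = 0 and 75.8% at q = 10% under failure scoring, a similar loss.

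**Unequal removal under failure scoring**

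- 5% in TWO₂ and none in control: 0.64×0.95 − 0.43 = 17.8 points.
- None in TWO₂ and 5% in control: 0.64 − 0.43×0.95 = 23.15 points.
- No true effect (43% in both arms), with 10 points more removal in one arm: 0.43×0.10 = 4.3 points of spurious difference. With 10% removed in one arm and none in the other, the simulated chance of rejecting at any of the three looks rises from 5.6% to 9.2%.

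**The case against.** The best case for the plan is that three sections already give the intended rule, and 8.2.6, the dedicated withdrawal section, states it for all subjects. The clause in 4.3 is permissive and does not forbid visits. This shows what was meant, but it leaves two instructions in force.

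A reader might infer that harms, amputations and closure in these subjects simply go unobserved. The documents do not support that. Adverse events are recorded weekly until removal, so an event that led to non-compliance before removal should already be on file. Section 4.3 lists adverse events as a separate ground for withdrawal, calls for a final evaluation, and has complaints and the reason for termination recorded. Section 7.2.10 follows serious effects, and non-serious effects possibly related to treatment, until they resolve or stabilize, beyond the end of the trial if needed. What remains exposed is week-12 closure, and new events and amputations after the final evaluation. An evaluation at removal is not a week-12 outcome.

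A reader might also infer that everyone must be followed to the end of the study. Section 9.2 reaches only to week 12. Beyond that the conflict is with 3.1, which asks subjects to return, and with 8.2.6, which says wherever possible.

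Finally, a reader might take a shift in the treatment difference as established. It depends on the scoring rule and on healing in those removed. Under omission, with closure at the arm's rate, the expected difference stays at 21 points and only power falls. Under failure scoring, if TWO₂ subjects who do not use the device close at 43% while the arm total stays 64%, then 10% removal in both arms gives (64 − 4.3) − (43 − 4.3) = 59.7 − 38.7 = 21.0 points, which is no change. Nor does 4.3 define non-compliance; the visit schedule assesses both treatment and dressings.

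**Conclusion.** The inconsistency is real. Section 4.3 excepts subjects removed for non-compliance from continued visits and only permits visits for the others; 3.1, 8.2.6, 9.2 and the premise of 9.1 say otherwise. Where a site applies 4.3, the primary outcome and later events may be missed in consenting subjects for a reason that arises after randomization.

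The size is conditional. At an assumed 10% unobserved per arm, fixed-sample power falls by about 10 points under failure scoring or about 5 under omission. The first figure also assumes closure at the arm's rate. Under failure scoring, a 10-point imbalance in removal produces a 4.3-point difference with no true effect. The planned 110 per arm is correct on its own inputs and is not in question here. The documents do not show how many subjects would be affected, nor the direction of any bias.

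**What to change.** Reconcile 4.3 with 3.1, 8.2.6 and 9.2:

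1. Strike the exception for non-compliance in 4.3, and change the permission to continue visits into a statement that subjects will be asked to continue, as 3.1 already does for those withdrawn by the investigator.
2. State that non-compliance may affect membership of the per-protocol set but does not end study follow-up while consent stands. Adjust the sentence in 4.3 on withdrawal from the study to agree.
3. Make 9.2 and 9.5 give one rule for an unobserved week-12 outcome in the primary analysis, and say whether it covers a subject who is contactable but was not followed.

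This concerns data collection only. When device treatment stops is outside the point, and no rule on it is proposed.

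The cost is a few sentences of protocol text, site retraining, and a few more contacts with poorly adherent subjects at visits already in the schedule.

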5. RANDOMIZATION

The Sponsor will act as the central randomization center. After successful assessment of inclusion/ exclusion criteria at the 2 week run in visit, the subject will be randomized to one of two treatment arms: TWO₂ group or, Control group. Study sites will notify the Sponsor when a subject has met the criteria for randomization. In accordance with local requirements, the device service provider will be notified by the study site , who will provide the contact details of the subject for device delivery, set-up and training.

Randomization will then be centrally performed by the Sponsor by utilizing randomized permuted blocks of number using the ralloc function in Strata 11.0 Subjects will be randomized to the next available treatment group. The local Device Service Provider will be notified of the assigned device, by the Randomisation Centre, to be delivered directly to the successfully randomized subject. The Central Reading Centre, Investigators and Trial monitors will not be aware of the randomization group assigned.

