All subjects will receive 90 minutes of either TWO₂ therapy or control therapy at their home or nursing care facility 5 times a week for the treatment phase of up to 12 weeks. To secure double blinding no TWO₂ treatment will be done at the study centers. Delivery, installation and training on use of the TWO₂ device or control device may differ according to geographical location and shall be performed by trained accredited home health service providers utilizing nurses or other registered healthcare providers, or by trained home/durable medical equipment (DME) providers and an expert on the TWO₂ device or control device. The subject, or in some cases caregiver or healthcare professional (such as a home health nurse or aide), applying the TWO₂ therapy or control therapy will be adequately trained and assessed for competency on the use of the device, which will be reviewed monthly. Dressing changes at home (or equivalent) may be performed either by the subject, caregiver or healthcare professional such as a home health nurse or aide. Both the TWO₂ therapy and control therapy groups will visit the study center once per week for on

treatment study visits. Dressings will be pre-specified advanced moist wound therapy (AMWT) dressings, which will be changed at a minimum of once weekly according to the PI/Subl Investigator's (Subl) clinical judgment. Subjects will receive standardized off-loading for a weight bearing wounds or an open heel boot for posterior heel wounds. A Charcot Restraint Orthotic Walker boot (CROW boot) may be used where there is a need to protect a Charcot Foot deformity. Debridement will be performed as needed according to the PI/Subl clinical judgment.

The treatment phase of the study will be 12 weeks. At every on treatment study visit at the clinic, foot ulcers are photographed. The initial (baseline) measurement after debridement will serve as the standard. Digital images will be sent to a blinded central assessor to be assessed and measured.

Once wounds are initially considered closed, that visit will serve as the first of two confirmatory visit. All subjects will continue treatment for an additional 2 weeks, to confirm wound closure.²³ During this period, subjects will continue to receive TWO2 therapy or Control therapy, use and change dressings, and use the off-loading device, where it is required, per the protocol. For subjects whose wounds close at week 11 or later the treatment phase will continue to the second confirmatory visit.

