5.2. Allocation concealment

Randomization will be coordinated by a central randomization center. Neither investigator nor subject will know their randomization allocation or can influence their allocation (=allocation concealment).

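### Section 5 tells the device service provider which device was assigned and leaves provider staff outside the blind, although they train the subject at home; coded devices would close this avoidable route to unequal support or disclosure.

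*Combined protocol and SAP*

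**What the plan says.** Section 5 places randomisation with the sponsor: "The Sponsor will act as the central randomization center". Once a subject qualifies, the site alerts the device service provider and passes on the subject's contact details ("who will provide the contact details of the subject for device delivery, set-up and training"). The randomisation is done after that, and then: "The local Device Service Provider will be notified of the assigned device, by the Randomisation Centre, to be delivered directly to the successfully randomized subject".

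Section 5 goes on, in its next sentence, to list who is kept unaware: "The Central Reading Centre, Investigators and Trial monitors will not be aware of the randomization group assigned". Section 5.2 adds: "Neither investigator nor subject will know their randomization allocation or can influence their allocation".

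Section 3.1 describes the work in the home. Depending on location, delivery, installation and training "shall be performed by trained accredited home health service providers utilizing nurses or other registered healthcare providers", or are done by equipment (DME) providers with a device expert. Therapy is applied by the subject, "or in some cases caregiver or healthcare professional (such as a home health nurse or aide"). On wound care: "Dressing changes at home (or equivalent) may be performed either by the subject, caregiver or healthcare professional such as a home health nurse or aide".

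Section 8.2.4 puts device competency checks in the home at weeks 4 and 8, without naming the assessor. Section 6.2 says the control looks and behaves like the active device; its controller is modified so that no oxygen or pressure reaches the limb while the display imitates therapy. Under section 7.1.1 closure is judged by the investigator, with a photograph reviewed by the central assessor.

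**The concern.** The trial is described as double blinded, and section 3.1 keeps device treatment out of the study centres to protect that. The plan thus recognises that contact between staff and the device threatens the blind. At home, however, the organisation that is told the assignment also sets up the device and teaches the subject to use it.

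A trainer who knows that a controller is a sham may, without intending to, give less encouragement or let the arm slip. If the same person, or a colleague, also gives wound care, dressings and reinforcement of off-loading could differ by arm. Section 6.3 itself says that standard care has a profound effect on outcome in chronic wounds. A subject who learns the arm could behave differently, withdraw, or tell the investigator who judges closure. Blinding at the clinic does not prevent differences in care that arise at home.

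**Working it through.** The plan gives no figure on this point, so the main check is a comparison of its passages.

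**Who is told, who is blinded, and who has contact at home**

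| Party | Told the assigned device? | Stated to be unaware? | Role in the home |
|---|---|---|---|
| Device service provider | Yes (section 5) | No | Delivery, set-up, training (sections 3.1, 5) |
| Home nurse or aide | Not stated | No | May apply therapy and change dressings (section 3.1) |
| Competency assessor, weeks 4 and 8 | Not stated | No | Home visit (section 8.2.4) |
| Subject | No | Yes (section 5.2) | Uses the device |
| Investigator | No | Yes (sections 5, 5.1, 5.2) | None; judges closure at clinic |
| Central reader | No | Yes (section 5) | None; reviews photographs |
| Trial monitors | No | Yes (section 5) | None |

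1. The provider is told the assigned device and is missing from both statements of who is unaware.
2. No section mentions a coded device number, a key linking number to arm, or a duty on provider staff to conceal the arm. The plain reading is that the provider learns TWO₂ or Control, but the text does not exclude a coded notice.
3. Section 3.1 lets a nurse or aide apply therapy and change dressings. It neither says that this person works for the provider nor rules it out. Overlap is permitted, not stated.
4. Section 6.2 puts the difference between devices inside the controller, so labelling by serial number looks feasible.

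**Illustration of what a shift in closure would do**

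Inputs from section 9.1: control closure 43%; three looks; p<0.022 at each; 110 per arm at the end. Section 9.6 sets the interim looks at 73 and 146 subjects, so about 37 and 73 per arm. The test is the uncorrected chi-square of section 9.3, applied at all three looks.

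The 110 reproduces. With n = [z(1−α/2)·√(2p̄q̄) + z(1−β)·√(p₁q₁+p₂q₂)]²/(p₁−p₂)², α = 0.022, 80% power, 43% v 64% and p̄ = 0.535:

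- numerator: (2.290×0.7054 + 0.8416×0.6896)² = 2.196² = 4.822
- n = 4.822/0.0441 = 109.3, so 110 per arm

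Assumed input, not from the documents: the device has no effect, but unequal home support or disclosure adds 0, 3, 5 or 8 percentage points to closure in the active arm. Simulated chance of crossing the boundary in favour of TWO₂ at any look:

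| Closure, control v active | False positive favouring TWO₂ |
|---|---|
| 43% v 43% | about 2.7% |
| 43% v 46% | about 6% |
| 43% v 48% | about 10% |
| 43% v 51% | about 20% |

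Any bias of the same size would give the same figures. They show the test's sensitivity to a shift and say nothing about how likely this route is to produce one.

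**The case against.** The case for the plan as written is substantial, and much of it stands.

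- **Endpoint assessment.** The investigator, subject and central reader are all stated to be blinded. A reader might infer that the double-blind label fails or that closure is judged unblinded; the documents do not support that.
- **Knowledge of the arm.** A reader might infer that home staff do know the arm. The notice concerns the assigned device and could be a coded unit. The text supports only that provider staff can know.
- **Wound care by the provider.** A reader might infer that the provider's own nurses change dressings. Section 3.1 does not link the two, and on the DME route no nurse is named.
- **A line back to the site.** The contact in section 5 runs from site to provider and comes before randomisation. The assignment then goes from the randomisation centre to the provider and the device goes straight to the subject. No reporting channel from provider to site is described.
- **The sponsor.** Holding the list does not by itself unblind sponsor monitoring. Section 10.3 describes the study monitor as representing the sponsor, and section 5 blinds monitors. Nothing says that the study director holds the list. What is missing is a statement separating whoever does hold it from other trial functions.
- **Limits on differential care.** Section 6.3.3 restricts dressings to a short list, and section 6.3.2 places off-loading education at the weekly wound assessment.
- **Size.** The 3-, 5- and 8-point shifts have no source in the documents. With no device effect, differing adherence to the device could not change closure, so only wound care, off-loading or disclosure could act in that scenario.

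These points narrow the concern without removing it. The provider is told the assignment, trains the subject, and is under no stated blinding or concealment duty.

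**Conclusion.** The concern holds as a limited and avoidable weakness in blinding. Section 5 informs the provider of the assigned device, and no section codes the device, blinds provider staff, binds them to conceal allocation, or separates them from home wound care. The remaining risk is unequal support at home or disclosure to the subject, not direct unblinding of the endpoint assessor.

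The size of any bias cannot be derived from the documents. The simulated rates of about 6%, 10% and 20% rest on assumed shifts and on no true device effect; they are illustrative only.

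The conclusion assumes that the notice is not already coded. If it is, a sentence saying so, with the blinded list extended to match, is enough. The change is worth making because the procedure is explicit, the safeguard is cheap, and section 6.2 indicates that coding is feasible.

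**What to change.** Amend section 5 as follows.

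1. The randomisation centre notifies the provider only of a coded controller serial number. Controllers are coded before shipment, and the serial-to-arm key is held by the randomisation function alone.
2. Add provider staff, trainers, and home nurses or aides to the parties stated to be unaware of the group.
3. Anyone who must be unblinded for technical reasons gives no training or wound care and does not discuss allocation.
4. State that the sponsor's key-holder has no monitoring, event-review or data-handling role.

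The cost is serial-number coding and a short amendment. Replacing a device after a malfunction would have to go through the key-holder. Because the control delivers no pressure to the limb, experienced staff may still recognise it in use, so coding reduces the risk but may not remove it.
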